#### 15.3.6.10. Pittsburgh Sleep Quality Index

Observed PSQI global score at the PS Baseline, OLE Baseline, and each scheduled post-OLE Baseline extension visit that it is scheduled for collection, including the Week 24 LOCF endpoint, will be summarized. Changes from Baseline in PSQI global score will also be summarized for each scheduled post-OLE Baseline extension visit, based on both the PS Baseline and the OLE Baseline.

#### 15.3.6.11. Subgroup Analysis (Safety Parameters)

Selected safety data will be summarized by subgroups of geographic region, sex, age, number of prior hospitalizations for treatment of schizophrenia, and duration of schizophrenia. Further details of subgroup analysis of the safety data will be provided in SAP, as needed.

#### 15.3.7. Pharmacokinetic Analysis

Plasma concentrations of SEP-363856 will be presented in a data listing. Population pharmacokinetic (POPPK) analysis will be performed using plasma concentrations of SEP-363856, the results of which will be reported separately.

# 15.3.8. Pharmacodynamic Analysis

The relationship between PANSS total score and plasma concentrations of SEP-363856 will be explored using POP-PK/pharmacodynamics (PD) methods, the results of which will be reported separately.

#### 15.3.9. Interim Analysis

None planned.

# 15.3.10. Treatment of Missing Data

For scales with more than one item, such as PANSS, if any item score contributing to the total/subscale score is missing, the total/subscale score will be set to missing.

Missing data at Week 24 will be imputed using the LOCF approach. The LOCF endpoint is defined as the last non-missing value at a scheduled or unscheduled visit post-baseline during the treatment period excluding the Follow-up Visit.

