# 11.4.1. Positive and Negative Syndrome Scale (PANSS)

The PANSS is an interview-based measure of the severity of psychopathology in adults with psychotic disorders. The measure is comprised of 30 items and 3 subscales: the Positive subscale assesses hallucinations, delusions, and related symptoms; the Negative subscale assesses emotional withdrawal, lack of motivation, and similar symptoms; and the General Psychopathology subscale addresses other symptoms such as anxiety, somatic concern, and disorientation. An anchored Likert scale from 1 - 7, where values of 2 and above indicate the presence of progressively more severe symptoms, is used to score each item. Individual items are then summed to determine scores for the 3 subscales, as well as a total score. A Composite scale score (Positive scale score minus Negative scale score) can also be calculated to show the relative valence of positive and negative symptoms. Total time required for the PANSS interview and scoring is approximately 30 to 40 minutes (Kay-1994, Opler-1992; Perkins-2000). The PANSS requires input from an informant (eg, caregiver, relative, friend, case worker, or hospital staff). PANSS interviews will be audio recorded and the recording may be reviewed by Sponsor's designee to monitor the quality of the rater interviews, where allowed by local/regional regulations. No identifying information will be associated with the audio recording. PANSS raters will be required to meet specific training and education criteria before they are certified to rate for this study.

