7. CGI-S
8. CGI-I
9. PSQI
10. SF-12
11. MSQ

Note: Rating assessments will be performed by the rater or subject using an electronic tablet. In the event that the electronic tablet is not available or assessment not available on the tablet, the rating assessments will be performed by the rater or subject using a paper version of the assessment.

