# 11.6.5. Visit 5E (Week 16; Day 113 $\pm$ 3 days) – Treatment Period

- Collect concomitant medications
- Vital sign measurements
- Weight (BMI derived in the electronic data system)
- Urine sample for β-hCG (for female subjects)
- PANSS
- CGI-S
- CGI-I
- BNSS
- C-SSRS

- Collect adverse events
- Study drug accountability
- Dispense study drug

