## 11.6.6. Visit 6E (Week 20; Day $141 \pm 3$ days) – Treatment Period

The following procedures will be conducted during this visit:

- Collect concomitant medications
- Vital sign measurements
- Weight (BMI derived in the electronic data system)
- Urine sample for  $\beta$ -hCG (for female subjects)
- C-SSRS
- Collect adverse events
- Study drug accountability
- Dispense study drug

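### Minor, cheap improvement: one missing item voids a multi-item score, so a Week 24 PANSS with 29 of 30 items is dropped and, at the LOCF endpoint, normally replaced by the Week 16 total

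*Protocol*

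**What the plan says.** Section 15.3.10 (Treatment of Missing Data) sets a rule for every scale with more than one item and names PANSS as its example: "if any item score contributing to the total/subscale score is missing, the total/subscale score will be set to missing". It gives no minimum number of items and no proration. The next paragraph adds "Missing data at Week 24 will be imputed using the LOCF approach" and takes as the carried value "the last non-missing value at a scheduled or unscheduled visit post-baseline during the treatment period", leaving out the Follow-up Visit.

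Section 11.4.1 describes the PANSS: "The measure is comprised of 30 items and 3 subscales", each item rated on "An anchored Likert scale from 1 - 7". Section 15.3.5 summarises the effectiveness scores at each scheduled extension visit and, separately, at the Week 24 LOCF endpoint. It does the same for PANSS response, a fall of at least 20% in the total from pre-switch (PS) Baseline. Section 15.3.5.3 confirms that effectiveness is descriptive only.

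Under section 11.6 ratings are made on an electronic tablet. If the tablet or the assessment on it is unavailable, "the rating assessments will be performed by the rater or subject using a paper version of the assessment".

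**The concern.** The two sentences of 15.3.10 act in sequence. The first turns a small gap (one unrated item) into a missing total. The second fills that gap at the Week 24 endpoint with a rating from an earlier visit, although the subject attended and nearly everything was rated. A nearly complete current observation gives way to a complete but older one.

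What is at stake is the precision and coherence of the Week 24 descriptive tables for PANSS, BNSS and the other multi-item scales, and of the PANSS response rate. No hypothesis test or decision rule depends on them. The primary endpoint (incidence of AEs, SAEs and AEs leading to discontinuation, section 15.3.6.1) does not use these scores.

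**Working it through.** **Planned size.** The synopsis and section 15.1 imply 120 × 0.75 × 0.75 = 67.5, which agrees with the stated figure of about 67. It is used below only to turn shares into subjects, as if all 67 were rated at Week 24.

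**Tracing the rule through the schedule** (Table 2; sections 11.6.2 to 11.6.7). With all visits attended and no later unscheduled rating, one missing item at Week 24 leads to:

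| Score | Earlier scheduled post-baseline ratings | Value used at Week 24 LOCF | Age of value |
|---|---|---|---|
| PANSS, BNSS total | Weeks 4, 8, 16 | Week 16 | 169 − 113 = 56 days |
| PSQI global | Week 12 | Week 12 | 169 − 85 = 84 days |
| AIMS total | Week 4 | Week 4 | 169 − 29 = 140 days |
| SF-12 | none | stays missing | – |

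SAS is analysed as a mean score (section 15.3.6.9), so whether a rule worded for totals and subscales covers it is unclear.

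**Two side effects.**
- Only scores containing the missing item are lost. A subject's LOCF total may come from Week 16 while two of the three subscales come from Week 24, so the parts need not sum to the total.
- LOCF uses post-baseline values only. A missing item at a baseline cannot be filled, and it removes the subject from every change from that baseline; at PS Baseline it also removes the subject from PANSS response.

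**How often.** The documents give no item-missing rate. For an assumed rate p, independent across items, the share of totals lost is 1 − (1 − p)^k, with k items:

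| p (assumed) | PANSS, k = 30 | of 67 | BNSS, k = 13 |
|---|---|---|---|
| 0.05% | 1.5% | about 1 | 0.7% |
| 0.1% | 3.0% | about 2 | 1.3% |
| 0.5% | 14.0% | about 9 | 6.3% |

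This is a range, not an estimate. Gaps that cluster within a rating affect fewer scores at the same p.

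**Error of proration, one PANSS item missing.** The prorated total is S × 30/29, where S is the sum of the 29 rated items. Its error is S/29 − x, where x is the unrated item. With item SD 1.2 and inter-item correlation ρ (both assumed) and equal item means, the variance is 1.2² × (1 − ρ) × (1 + 1/29):
- ρ = 0.1: 1.44 × 0.9 × 1.0345 = 1.34, RMSE 1.16 points.
- ρ = 0.3: 1.44 × 0.7 × 1.0345 = 1.04, RMSE 1.02 points.

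For true totals of 45 to 90 (assumed range) the extremes are (45 − 7) × 30/29 − 45 = −5.7 and (90 − 1) × 30/29 − 90 = +2.1. Since items run from 1 to 7, the error with one item missing can never exceed 6 points.

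At the limit of 27 of 30 items the variance is 1.44 × (1 − ρ) × (9/27 + 3), giving an RMSE of 2.1 points (ρ = 0.1) or 1.8 points (ρ = 0.3).

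**Error of carrying Week 16 forward.** This is the subject's eight-week change, taken as an SD of 6 to 10 points (assumed).

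**Effect on the Week 24 LOCF mean.** With 2 to 9 subjects affected, the added random error is √2 × 6/67 = 0.13 to √9 × 10/67 = 0.45 points. An assumed systematic shift of 3 points between Weeks 16 and 24 would move the mean by 2 × 3/67 = 0.09 to 9 × 3/67 = 0.40. For an assumed SD of change of 10 to 15, the standard error of the mean is 10/√67 = 1.2 to 15/√67 = 1.8.

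**The case against.** The strongest defence is that nothing here is wrong in itself. A complete-items rule is explicit and reproducible, avoids inventing ratings, and is contradicted nowhere in the protocol. That stands: this is a choice of method, not an error.

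Gaps may also be rare. Ratings are made on a tablet, PANSS raters are certified, and interviews are recorded for possible quality review. This is plausible, although the protocol does not say that complete entry is forced, and it does provide for paper.

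A reader might infer that Week 24 results are broadly replaced by eight-week-old values, or that up to 14% of PANSS totals will be lost. The documents support neither. Replacement occurs only at the LOCF endpoint; the by-visit table simply omits the score. Eight weeks holds for PANSS and BNSS, but not for PSQI or AIMS. The 14% rests on an assumed rate.

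Proration has limits too. The 90% threshold is a judgement without a source in the protocol. It does not suit very short scores: the BARS total sums three items (section 11.3.6.2), so one missing item leaves 67%. Baseline scores come from SEP361-308, whose scoring rule is not shown, so prorating only the extension visits could score baseline and follow-up differently. The fix has to respect these points.

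**Conclusion.** The point holds as a minor, cheap improvement. As written, section 15.3.10 discards a nearly complete Week 24 PANSS and, at the LOCF endpoint, normally substitutes the Week 16 total. For an affected subject, proration is the more accurate choice: about 1 point of typical error with one item missing, against an assumed 6 to 10 points for the carried value.

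For the study, the effect is small. It is confined to descriptive summaries and the PANSS response rate, and under the assumptions shown both the random error and the shift in the Week 24 mean stay well below its standard error. The mechanism follows from the text; the sizes rest on assumed missing-item rates, item SD, correlation and eight-week change. A SAP could still add a proration rule, but the protocol fixes the stricter one.

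**What to change.** In section 15.3.10:

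- Prorate the PANSS and BNSS totals when at least 90% of items are present (PANSS at least 27 of 30; BNSS at least 12 of 13, which is 92%), and set them to missing below that.
- Apply the same rule to item-level data at PS Baseline, OLE Baseline and every extension visit, so that changes compare like with like.
- Keep the complete-items rule for very short scores such as the three-item BARS total.
- Report the number of prorated scores by visit, and show the result under the current rule as a check.

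A PANSS subscale that contains the missing item would still follow the complete-items rule, so a table footnote should say that total and subscales may rest on different visits.

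The cost is a few sentences and minor programming before database lock. The downside is the proration error in the few affected scores (typically about 1 point and at most 6 with one PANSS item missing; about 2 points typically with three) and a possible difference from the scoring convention used in SEP361-308.

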- j Subjects must be fasted (no food or drink except water at least 8 hours prior to clinical laboratory tests). A list of clinical laboratory tests is provided in Section 21.
- k Blood samples for plasma concentrations of SEP-363856 will be collected on Day 29, Day 85 and Day 169/EOT/ET. The time and date of the previous dose of study drug prior to blood sampling and the time and date of blood sampling must be recorded. The remaining plasma samples, after PK measurement is completed, CCI
-  Urine drug screen may be ordered at other visits as deemed clinically appropriate. These results should be discussed with the Medical Monitor.
- m Any positive urine β-hCG test should be confirmed by a serum β-hCG test.
- n Unscheduled SAS, BARS and AIMS scales should be administered if a subject develops extrapyramidal symptoms requiring treatment.
- o Any new AEs occurring after signing the informed consent form for this study (SEP361-309) at V1E will be collected. Adverse events with onset during the Core study (SEP361-308) and ongoing at the start of the current study (SEP361-309) will be entered into the eCRF.

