#### 15.3.5. Effectiveness Analyses

Effectiveness data will be summarized descriptively for the safety population.

The observed values of PANSS total score and subscale scores (positive, negative, and general psychopathology), PANSS Marder Factor (five-factor) scores, Uncorrelated PANSS (seven-factor) Score Matrix (UPSM), CGI-S score, CGI-I, BNSS total score, SF-12 score, PSP score, and MSQ score, at the PS Baseline, OLE Baseline, and each scheduled post-OLE Baseline extension visit, including the Week 24 last-observation carried forward (LOCF) endpoint, will be summarized descriptively. Changes from Baseline in these efficacy measures will be summarized at each scheduled post-OLE Baseline extension visit and Week 24 LOCF endpoint, based on both the PS Baseline and the OLE Baseline.

PANSS total score and CGI-S score data will also be summarized by age, sex, race, number of prior hospitalizations for treatment of schizophrenia, duration of schizophrenia, geographic region, and country.

The proportion of subjects who achieve a response, defined as a 20% or greater improvement (ie, decrease) in PANSS total score from the Baseline, will be calculated for each scheduled visit and the Week 24 LOCF endpoint based on the PS Baseline of study SEP361-308.

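### LOCF is the only handling of missing Week 24 data, so early leavers can count as Week 24 responders and values from discontinuation or before stand in for 24-week results

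*Protocol*

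**What the plan says.** Protocol Section 15.3.10 sets one rule: "Missing data at Week 24 will be imputed using the LOCF approach". The value carried is the "last non-missing value at a scheduled or unscheduled visit post-baseline during the treatment period", with the Follow-up Visit left out. The same section voids a total or subscale score if any contributing item is missing.

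Section 15.3.5 defines response on the PANSS, "defined as a 20% or greater improvement (ie, decrease) in PANSS total score from the Baseline", and says the proportion "will be calculated for each scheduled visit and the Week 24 LOCF endpoint based on the PS Baseline of study SEP361-308". For the scores themselves, "Changes from Baseline in these efficacy measures will be summarized at each scheduled post-OLE Baseline extension visit and Week 24 LOCF endpoint". Sections 15.3.6.3, 15.3.6.5, 15.3.6.9 and 15.3.6.10 use the same Week 24 LOCF endpoint for laboratory values, vital signs, motor scales and PSQI.

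Four other places bear on how the rule works:
- Table 2 schedules PANSS, CGI-S and BNSS at Weeks 4, 8, 16 and 24/ET, and SAS, BARS and AIMS at Weeks 4 and 24/ET only.
- Table 2, footnote b, asks for all ET procedures within 48 hours of the last dose.
- Table 2, footnote n: "Unscheduled SAS, BARS and AIMS scales should be administered if a subject develops extrapyramidal symptoms requiring treatment".
- Section 13.1 removes from the study anyone who is taken off drug.

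**The concern.** Section 7.3.3 gives the aim as showing that switched patients can be maintained safely and effectively for 24 weeks. A subject who improves, then stops for an adverse event or is lost to follow-up, was not maintained. If the last rating still meets the 20% criterion, that subject nevertheless enters the numerator of a rate labelled Week 24. Nothing later corrects this, because no ratings follow the ET visit.

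The age of the carried value is a second issue. With an ET rating, it is the value at discontinuation. Without one, or if an ET PANSS is voided by a missing item, the rule reaches back to an earlier visit. For the motor scales that is Week 4, unless an unscheduled rating exists. The protocol directs unscheduled motor ratings only when extrapyramidal symptoms need treatment.

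At stake is how the long-term effectiveness results, and the Week 24 summaries of the other measures, will be read. The by-visit summaries cover only subjects still rated at each visit, and the LOCF endpoint assumes no change after leaving. Neither gives the proportion of the safety population that was on treatment and responding at Week 24.

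**Working it through.** **1. Planning figure.** Section 15.1 expects about 67 subjects. From the core study's planned 120: 120 × 0.75 × 0.75 = 67.5, which agrees. No power calculation applies, because the study is single-arm and descriptive.

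**2. Direction.** Let N be the safety population, c the responders among subjects with a Week 24 PANSS, and r the leavers whose last value meets the criterion.
- LOCF rate = (c + r)/N
- Leavers as non-responders = c/N
- Excess = r/N, which cannot be negative

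If subjects with no post-baseline PANSS drop out of the LOCF denominator, the LOCF rate only rises.

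**3. Dropout range (assumed).** The protocol gives no dropout rate for the extension. Three illustrative sources:
- 25%, a round lower value.
- 31% to 39%, from the 70% to 80% discontinuation before 18 months cited in Section 4.1. At constant hazard, taking 18 months as 78 weeks: 1 − 0.30^(24/78) = 0.310 and 1 − 0.20^(24/78) = 0.391.
- 58%, from the core study's assumed 25% loss in 8 weeks repeated three times: 1 − 0.75³ = 0.578.

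**4. Response rates.** N = 67. Assumed: half of completers respond, and 20% to 60% of leavers meet the criterion at their last rating. Counts are rounded to whole subjects.

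| Dropout | Leavers / completers | Completers responding | Leavers responding (20%–60%) | LOCF rate | Leavers as non-responders | Excess (points) |
|---|---|---|---|---|---|---|
| 25% | 17 / 50 | 25 | 3–10 | 41.8%–52.2% | 37.3% | 4.5–14.9 |
| 31% | 21 / 46 | 23 | 4–13 | 40.3%–53.7% | 34.3% | 6.0–19.4 |
| 39% | 26 / 41 | 20 | 5–16 | 37.3%–53.7% | 29.9% | 7.5–23.9 |
| 58% | 39 / 28 | 14 | 8–23 | 32.8%–55.2% | 20.9% | 11.9–34.3 |

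The excess depends only on the number of leavers who respond, not on the completer response rate.

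**5. Age of carried values.** A subject lost after Week 4 (Day 29) without an ET rating has that value carried to Day 169: 169 − 29 = 140 days, or 20 weeks. A PANSS carried from Week 16 is 8 weeks old at Week 24.

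**6. Change scores (illustrative).** Suppose a measure drifts linearly, the hazard of leaving is constant and every leaver is rated on leaving. The LOCF mean then shows (1 − e^(−λT))/(λT) of the full change, with λT = −ln(1 − d) for dropout d.
- d = 0.310: 0.310/0.370 = 0.84
- d = 0.391: 0.391/0.495 = 0.79

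Measured from the pre-switch baseline 8 weeks earlier, at the same rate of drift, the shares are (8 + 24 × 0.836)/32 = 0.88 and (8 + 24 × 0.789)/32 = 0.84.

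**The case against.** The strongest defence is the ET visit. It repeats the scheduled scales close to the last dose, so for a leaver who attends, the carried value is the rating at discontinuation and can capture worsening. That stands. Values as old as Week 4 arise only when the ET assessment is missed or unusable. It does not answer the response point, because someone who stops for intolerability while still improved counts as a responder even with a perfect ET visit.

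The protocol also labels the endpoint openly as LOCF, plans by-visit summaries and treats effectiveness as descriptive (Section 15.3.5.3). Method detail can go in the SAP, which was not available here. These points limit the weight. But the protocol does not leave the method open: it names LOCF and nothing else.

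Three stronger readings are tempting, and the documents do not support them:
- *The response rate is inflated by symptom-triggered unscheduled ratings.* Such ratings are specified only for SAS, BARS and AIMS. At dose-adjustment visits a PANSS is merely permitted (Section 11.6.10). One done because response was inadequate would tend to lower the rate.
- *The excess is 15 to 20 points.* That needs half of leavers to be responders, which has no source. It also borrows dropout from a background outpatient study, whereas this sample consists of 8-week completers who chose to continue.
- *The rate is biased upward in an absolute sense.* The direction is certain only against counting leavers as non-responders. That is a choice of what to estimate, although it is the one closest to the aim in Section 7.3.3.

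**Conclusion.** The point holds. As written, Sections 15.3.5 and 15.3.10 produce a Week 24 response rate that credits early leavers, and Week 24 means built partly on values from discontinuation or earlier. That the LOCF rate cannot fall below the leavers-as-non-responders rate follows from the definitions and needs no assumption.

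The size does rest on assumptions: about 4 to 34 points over 25% to 58% dropout with 20% to 60% of leavers responding. The protocol cannot narrow that range. The change-score shares in step 6 depend equally on assumed linear drift and constant hazard.

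The primary endpoint (incidence of adverse events, serious adverse events and those leading to discontinuation) uses no LOCF and is unaffected. No hypothesis test or error rate is involved. The change should be made because the aim is maintenance over 24 weeks and the remedy is cheap.

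**What to change.** Amend Sections 15.3.5 and 15.3.10 and carry the change into the SAP.

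(a) Report the Week 24 response rate in the safety population with subjects lacking a Week 24 PANSS counted as non-responders. State that an ET rating before the Week 24 window is not a Week 24 PANSS. Keep the LOCF rate as a sensitivity display labelled as the last on-treatment value, and show the observed Week 24 result with its denominator.

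(b) Add a mixed model for repeated measures for change in PANSS, CGI-S and BNSS. Map ET ratings to the nearest scheduled assessment visit. PANSS is not scheduled at Weeks 12 and 20, so without such a rule discontinuation ratings could be lost.

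(c) Keep unscheduled symptom-triggered SAS, BARS and AIMS ratings in the last on-treatment summary, and show the endpoint with and without them. Simply excluding them would be unsound: a leaver's last symptomatic score could be replaced by an older, symptom-free Week 4 score, which would understate harm.

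The cost is a wording change and modest programming, with no new data. The model brings a missing-at-random assumption, and the response rate will look less favourable.

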#### 10.3.1. Prohibited Medications

Newly administered psychotropic medications and newly administered medications with a propensity for psychotropic effects are not permitted during the Treatment Period up through the Follow-up Visit, with the exception of the medications discussed in Section 10.3.3. The use of herbal supplements, dietary supplements or other complementary or alternative medications for treating psychiatric indications is not permitted during the Treatment Period; however, is permitted after the last dose of study medication provided, they are not administered prior to the final PANSS assessment.

Use of psychotropic medications after the last dose of study medication is permitted provided, they are not administered prior to the final PANSS assessment.

Subjects who are administered a psychotropic medication (other than the study drug and the acceptable medications described in Section 10.3.3) for the purposes of treating an exacerbation of symptoms associated schizophrenia or due to lack of efficacy of the study treatment will be discontinued from the study.

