# 11.6.7. Visit 7E (Week 24 / End of Treatment / Early Termination; Day 169 ± 3 days) – Treatment Period

- Collect concomitant medications
- Physical and neurological examinations
- Collect nicotine use information
- Vital sign measurements
- Weight and waist circumference (BMI derived in the electronic data system)
- Perform standard 12-lead ECG
- Fasted blood samples for clinical laboratory evaluation (hematology and serum chemistry)
- Blood sample for PK
- Urine sample for urinalysis, UDS, and  $\beta$ -hCG (for female subjects)
- PANSS
- CGI-S
- CGI-I
- BNSS
- C-SSRS

- SAS
- BARS
- AIMS
- PSQI
- PSP
- SF-12
- MSO
- HCRU
- Collect adverse events
- Study drug accountability

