#### 13. TERMINATION OF SUBJECT FROM STUDY

# **13.1.** Criteria for Subject Termination

Subjects may be discontinued from study participation / the study drug at any time for any of the following reasons. The possible reasons for termination of study participation / study drug are as follows:

- Adverse event
- Lack of efficacy (specify)
- Lost to follow-up (specify)
- Withdrawal by subject (specify)
- Non-compliance with study drug (specify)
- Protocol deviation (specify)
- Death
- Pregnancy
- Other (specify)

If at any time during the course of the study, in the opinion of the Investigator, the subject may no longer safely participate due to a change in medical status (eg, experiences an AE, becomes pregnant), the subject must be discontinued from the study drug. Subjects discontinued from study drug will be discontinued from the study.

The reason for discontinuation of "Lack of efficacy" should be selected when a subject early terminates from the study because there has been insufficient therapeutic benefit of the study drug (perceived or actual) and the subject's baseline condition has neither worsened nor improved significantly.

The reason for study drug discontinuation will be recorded on the appropriate CRF. In case of death, the date of death should be captured on the CRF. Subjects who prematurely terminate the study participation will not be replaced.

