# 13.2. Clinical Assessments After Study Drug Discontinuation

Subjects who have not received any study drug will not be followed up on leaving the study.

For subjects who have received study drug and who prematurely discontinue from the study treatment (ie, do not complete through Week 24), every effort should be made to complete the final evaluation procedures, in accordance with the ET visit described in Section 11.6.7.

Subjects who complete the study and those subjects who discontinue the study early will complete a follow up visit 7 (±2) days after the last dose of study drug as described in Section 11.6.9.

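### A PANSS score taken after rescue with a non-allowed psychotropic can become the Week 24 LOCF value and count as a response to SEP-363856

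*Protocol*

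**What the plan says.** The relevant rules are spread over several sections of the Protocol.

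- **LOCF (15.3.10).** The endpoint is the "last non-missing value at a scheduled or unscheduled visit post-baseline during the treatment period excluding the Follow-up Visit".
- **Response (15.3.5).** The analysis counts subjects who "achieve a response, defined as a 20% or greater improvement (ie, decrease) in PANSS total score from the Baseline"; the proportion "will be calculated for each scheduled visit and the Week 24 LOCF endpoint based on the PS Baseline of study SEP361-308".
- **Rescue (10.3.1).** Subjects given a psychotropic outside the allowed list "for the purposes of treating an exacerbation of symptoms associated schizophrenia or due to lack of efficacy of the study treatment will be discontinued". Section 13.1 adds: "Subjects discontinued from study drug will be discontinued from the study".
- **Early-termination visit.** For subjects who stop early, "every effort should be made to complete the final evaluation procedures, in accordance with the ET visit described in Section 11.6.7" (13.2). That section is headed "Visit 7E (Week 24 / End of Treatment / Early Termination; Day 169 ± 3 days) – Treatment Period", and PANSS is on its procedure list. Footnote b to Table 2 sets a limit of 48 hours after the last study dose.
- **Order of PANSS and new medication (10.3.1).** "Use of psychotropic medications after the last dose of study medication is permitted provided, they are not administered prior to the final PANSS assessment".
- **Population (15.2.1).** Effectiveness is analysed in everyone who took at least one extension dose, so rescued subjects stay in.

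**The concern.** Section 7.3.3 frames the study around whether subjects who have been switched can be maintained effectively on SEP-363856. A subject who needed another psychotropic because of exacerbation or lack of efficacy was not maintained in that sense. Yet the only value that 15.3.10 excludes is the Follow-up Visit, and the only condition in 15.3.5 is the percentage fall in PANSS. If the last treatment-period PANSS was taken after the other drug had been started, any benefit from that drug is credited to SEP-363856. This affects the Week 24 LOCF mean and, if the 20% threshold is met, the responder count.

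Section 10.3.1 shows that the intent is for the final PANSS to come before other psychotropics. The analysis rules do not carry that intent through to cases where it was not achieved.

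**Working it through.** **Step 1: follow a rescued subject through the rules.**

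1. A non-allowed psychotropic is given for exacerbation or lack of efficacy while the subject is still on study drug, or otherwise before the last PANSS. Section 10.3.1 foresees such rescue and requires discontinuation.
2. The subject goes to the early-termination visit, which includes PANSS (11.6.7, 13.2). An unscheduled PANSS is also possible.
3. That visit is in the Treatment Period and is not the Follow-up Visit, so 15.3.10 accepts its score as the last non-missing value.
4. Section 15.3.5 compares the score with the pre-switch Baseline. A fall of 20% or more counts as a response.
5. Section 15.2.1 keeps the subject in the denominator.

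No step removes or flags the post-rescue score.

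**Step 2: check the safeguards.**

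| Safeguard | What it does | What it leaves open |
|---|---|---|
| Ban on new psychotropics (10.3.1) | Makes rescue on study drug a deviation | No instruction on the resulting PANSS |
| PANSS before other psychotropics (10.3.1) | Covers drugs taken after the last study dose | Not worded for rescue on study drug; no analysis rule |
| 48-hour limit (Table 2, footnote b) | Keeps the early-termination PANSS close to the last study dose | Runs from the study dose, not from the rescue dose |
| Deviation, disposition and medication tables (15.3.3, 15.3.1, 15.3.6.7) | Show that such subjects exist | Do not change the responder count or the LOCF mean |

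**Step 3: can these subjects be identified?** The discontinuation reason is not enough. Section 13.1 reserves the lack-of-efficacy reason for subjects with too little benefit whose condition has not changed significantly in either direction. An exacerbation therefore falls under another reason. Section 10.3, however, requires the start date, start time and indication of each medication, which identifies both groups.

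**Step 4: size.** The Protocol's own figure first: 120 parent-study subjects × 0.75 completing × 0.75 enrolling = 67.5, stated as about 67 (Synopsis; 15.1). This reproduces.

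The Protocol gives no rate of rescue before the last PANSS and no rescue effect, so the inputs below are assumptions.

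- Response rate, per reclassified subject: 1 / 67 = 1.5 percentage points.
- Response rate, 3 subjects: 3 / 67 = 4.5 points.
- Week 24 LOCF mean, low end (1 subject, 2 PANSS points): 1 × 2 / 67 = 0.03 points.
- Week 24 LOCF mean, high end (3 subjects, 10 PANSS points): 3 × 10 / 67 = 0.45 points.

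A much more generous assumption is that 5% to 15% of subjects are rescued before the PANSS and 25% to 75% of them meet the threshold. The shift is then 0.05 × 0.25 = 1.25 points at the low end and 0.15 × 0.75 = 11.25 points at the high end. Nothing in the Protocol supports rates that high.

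**The case against.** **This belongs in the SAP.** Section 15 leaves statistical detail to the SAP, which is not at hand and could add a rescue rule. That is fair as far as it goes. But the Protocol does not leave LOCF and response open: it states both in working form, and as stated they admit the score. An SAP rule would be amending them.

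**The route is narrow.** If the site stops study drug, does the PANSS and only then starts another drug, the problem does not arise. The 48-hour limit and the weekly calls that collect medications (11.6.8) shorten any exposure. This stands, and it is why few subjects are likely to be affected. A reader might infer that weeks of post-rescue scores enter the analysis. Mandatory discontinuation means that in practice it is the early-termination PANSS or an unscheduled one.

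**A false response is unlikely in any one subject.** The score must be at least 20% below the pre-switch Baseline, soon after an exacerbation or treatment failure. Many such subjects will score badly, and LOCF will carry that failure forward correctly. Others may have met the threshold before rescue. This also stands: the documents do not show that rescue would produce the response. They show only that nothing separates the two.

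**A rescue rule could reach too far.** Treating every subject who received another psychotropic as a non-responder would catch those medicated after their final PANSS. Section 10.3.1 permits that, and their score is uncontaminated. The objection is right, so the rule needs a timing condition.

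**Conclusion.** The gap is real and small. As written, 15.3.10 and 15.3.5 allow a post-rescue PANSS to become the Week 24 LOCF value and count as a response to SEP-363856 when rescue began before that PANSS. Each reclassified subject is worth about 1.5 percentage points of the response rate at 67 subjects. With 1 to 3 subjects affected (assumed), the rate moves by at most 1.5 to 4.5 points. The LOCF mean moves by 0.03 to 0.45 points if rescue is worth 2 to 10 PANSS points (also assumed).

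Two stronger readings are not supported. A reader might infer that the study's main conclusion is at risk. The primary endpoint is adverse-event incidence (6.1), response is not listed among the endpoints in 6.3, and effectiveness is descriptive without testing (15.3.5.3). A reader might also infer that the affected subjects cannot be found. The discontinuation reason misses those with exacerbation, but a subject rescued for lack of efficacy without significant worsening fits the lack-of-efficacy reason, and medication records identify both groups.

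The change is worth considering because it is cheap and matches the intent of 10.3.1. Confidence is moderate, since the SAP may already deal with it.

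**What to change.** Add one rule to 15.3.5, with a cross-reference in 15.3.10:

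- A subject whose first non-allowed psychotropic for exacerbation or lack of efficacy started before a treatment-period PANSS is a non-responder at that PANSS and at any later PANSS. The subject is also a non-responder at the Week 24 LOCF endpoint when the LOCF value comes from such a PANSS.
- Psychotropics started after the final treatment-period PANSS do not trigger the rule. Neither do the medications allowed under 10.3.3.
- Identify these subjects from the recorded start date, start time and indication, not from the discontinuation reason. Impute nothing at visits not attended.
- Keep these subjects in the main LOCF mean and report how many there are. A summary without them should be supplementary only, because dropping likely treatment failures could flatter the drug.

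Do not simply discard the post-rescue score. LOCF would then carry forward an earlier PANSS, possibly from before the exacerbation, which could look better still.

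The cost is one date and time comparison per PANSS on data already collected, and possibly a slightly lower response rate. The response measure also becomes a composite of PANSS change and freedom from rescue, which the report should state.
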